In contradistinction, the studies by Worda et al⁸ and Connor et al.^{16-21,26,31} have examined topical eyelid androgen application with generally favorable effects on tear film parameters and also a good safety profile. However, the eyelid application studies were not consistent in the subject type (e.g., both males and females were not uniformly enrolled), the androgen status and serum levels were not assessed prior to, or following androgen application and the studies were only published as peer-reviewed abstracts and mostly were done in one laboratory. This prospective randomized, controlled double masked study aims to evaluate the efficacy and safety of topical transdermal application to the eyelids of low dosage androgen in a population of patients with evaporative dry eye associated with meibomian gland dystrophy and aqueous tear deficient dry eye.

Methods

Study objective

To evaluate the safety and efficacy of an FDA-approved androgen nasal supplement (Natesto, Acerus Pharmaceuticals Corporation, 4.5% gel concentration) in males and females with dry eye of either aqueous tear deficiency or evaporative subtype.

Clinical hypothesis

- Natesto applied to upper and lower eyelid skin is more effective than placebo as measured by fluorescein tear breakup time (TBUT) and mean scores for meibomian secretion quality at 4 weeks and overall ocular comfort at 8 weeks.
- Natesto has an acceptable safety profile in ocular structures and general systemic system.

Statistical Hypotheses:

H₀: There is no difference in change from baseline to week four for either fluorescein breakup time (TBUT) or meibomian secretion score (0 - 24 scale) between the test and placebo-treated sample.

 H_A : There is a difference in the change from baseline to week four for either fluorescein breakup time (TBUT) or meibomian secretion score (0 – 24 scale) between the test and placebo-treated sample

Overall study design

Structure

We propose a randomized controlled trial (RCT) of one month duration dosing BID with

an FDA-approved androgen nasal supplement (Natesto, Acerus Pharmaceuticals

Corporation, 4.5% gel concentration) in males and females with dry eye of either aqueous tear deficiency or evaporative subtype.

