The test formulation will be marketed Natesto gel, containing 5.5 mg testosterone per pump (17 β -Hydroxyandrost-4-en-3-one; inactive ingredients are castor oil, oleoyl polyoxylglycerides and colloidal silicone dioxide; Natesto package insert). The placebo is the exact same formulation without 17 β -Hydroxyandrost-4-en-3-one. The drug and placebo will be delivered to and dispensed by Caduceus Medical group in Yorba Linda for MBKU's study use.

Dosage regimen

One dose per eyelid of masked gel, which is one pump from the dispenser, represents 5.5 mg for each eyelid, will be applied on the surface of upper and lower eyelid skin each eye twice per day (separated by 8 hours) for a total daily dose of 22mg.

Duration

2-week screening period; 4-week masked treatment phase, 8-week washout phase.

Overall study duration 14 weeks

Visit schedule (see Table 4 and 5)

- Visit 1: Screening visit (Day -14)
- Visit 2: Baseline (Day 0) : the drug (placebo) is prescribed and dispensed.
 Instructions are given on how to properly apply the drug. Subjects are instructed to keep the container even if the drug is finished. All containers need to be checked in the following two visits (visit 3 & 4)
- Visit 2a: serum blood draw for baseline total testosterone level, hematocrit, lipid panel, PSA for men only at clinical laboratory

- Visit 3: Two-week visit: check the drug (placebo) to see if supplement needed.
 Empty containers need to be collected.
- Visit 4: Week 4: the drug (placebo) is discontinued. All dispensed containers need to be collected.
- Visit 4a: serum blood draw for treatment period total testosterone level at clinical laboratory (must be in AM, and must be within two hours of application)
- Visit 5: Week 8: 4-weeks washout phase follow up
- Visit 6: Week 12: 8-week washout phase follow up

Evaluation criteria

Efficacy measures

Primary

- Fluorescein tear breakup time (FTBUT)
- MGD secretion grade (0-24 scale)

Secondary:

- 1. Schein Questionnaire and Ocular Surface Disease Index (OSDI)
- Corneal and conjunctival staining as per the Oxford and National Eye Institute (NEI) schemes
- Tear Meniscus Height (TMH) utilizing Keratography 5M (K5M Oculus, Inc Arlington,WA)
- 4. Eyelid signs grading of orifice metaplasia, vascularity, plugged orifice, lid margin irregularity, ridging between orifices, and antero-posterior orifice displacement
- 5. Meiboscore utilizing K5M
- 6. Schirmer I test without anesthetic

Exploratory:

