- In this present investigation the principal outcome measures, fluorescein TBUT (using 2.0 microliters of 1.0% sodium fluorescein) and the system for meibomian gland secretion (0-24 scale) are recommended by the MGD workshop and DEWS II diagnostic committees.⁴ Table 2 shows the sample size estimation with two arm parallel design, comparing the change from baseline in FTBUT in each arm with a two sample t-test continuous data, clinically meaningful change of 2.5 seconds with Standard Deviation (SD) following treatment of 2.5 seconds. The results are as follow:
- 2-Sample t Test
- Testing mean $1 = \text{mean } 2 \text{ (versus } \neq \text{)}$
- Calculating power for mean 1 = mean 2 + difference
- $\alpha = 0.05$
- Assumed standard deviation = 2.5

Table 2: Sample size estimation

_	Difference	Sample Size	Target Power	Actual Power
	2.0	26	0.8	0.807487
	2.5	17	0.8	0.807037
	3.0	12	0.8	0.802079
	3.5	10	0.8	0.841306

4.0

0.8

0.844793

- 2.
- 3. With the actual power of 0.807, total of 34 subjects with seventeen (17) subjects per arm will be recruited for this study.

8

Randomization method

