Informed		v /			,	,, , ,, , ,, , ,, , ,, , ,, , ,, , , , , , , , , , , , , , , , , , , ,
Consent /	Χ					
HIPAA						
Medical/C	N/					
L History	Х	X				
Ophthalm						
oscopy		X		Х		х
exam						
Visual						
Acuity	Х	X	X	X	X	X
Hair						
evaluation		X		X		X
Blood						
Pressure		X		X		Х
Blood						
draw for						
sex		Х		X		
hormone						
Questionn						
aires:						
OSDI,	Х	Х	Х	x	x	Х
Schein,						
MGD-						
Specific						
Biomicros						
copy:						
general,	х	Х	х	x	x	х
and lid	~	X		~	^	~
signs (0 –						
5 scale)						
Tear	Х	Х	х			Х
osmolarity	~	~	~			
NIBUT						
(Keratogr	Х	Х	Х	x	x	Х
aph)						
Tear						
meniscus						
height	Х	Х	Х	x	х	Х
(Keratogr						
aph)						
TBUT,						
seconds						
(fluorescei	Х	Х	х	x	x	х
n; nearest						
1/10 th)						

 Table 5: Schedule of visits and procedures

$\begin{tabular}{ c c c c } \hline \hline Corneal \\ Staining^a: \\ Both OSS \\ (0-12) \\ and NEI \\ (1995) \\ scale (0- \\ 33) \\ \hline \end{tabular}$	OSS and NEI	OSS and NEI	NEI X	NEI x	NEI X	NEI X
Conjuncti val Staining [,]	х	х	х	x	х	х
Total Staining, for Severity Purposes:	Х	Х	Х	x	х	х
Meibomia n Gland Excreta Grading (0-24)	х	х	Х	x	х	х
Gland Imaging:	Х			x		х
Schirmer I sans anesthetic; 5 mins	Х	X	X	x	X	X
IOP Drug or Placebo Applicatio n		x Initiate Drug or Placebo Applicatio n		x Halt Drug or Placebo Applicatio n		X

Procedure I: Enrollment

- Informed consent and HIPAA documentation and California Research Subject's Bill of Rights. We will discuss the study with subjects and check verbally that they have understood important points, particularly potential risks.
- Comprehensive Ocular and Medical History

- The history questionnaire, which includes questions on contact lens use as well as complete medical and ocular history, will be administered by the examiner and used to further determine whether the subject met the inclusion and exclusion criteria.
- Verify compliance with guidelines for visit preparation
- Best Corrected Visual Acuity (BCVA) (OD/OS)
- BCVA must be 20/25 (0.1 log MAR) or better OD and OS
- LogMAR chart, calibrated at a testing distance of ten feet, and Snellen Equivalent will be recorded.
- If the subject was deemed eligible to participate in the study, they will be asked to participate in Procedure II.

Procedure II: Dry Eye Work-up

- Symptomatology questionnaires (Appendix II Symptoms questionnaires):
- Schein questionnaire;⁴⁷a score of \geq 7.5 out of 24 indicates dry eye.⁴⁸

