Appendix III: Dry Eye Classification Criteria and Appendix V: Staging the Severity of MGD-Related Ocular Surface Disease

17. General statistical methods and types of analyses

- Comparisons, ANOVA, meibomian secretion scores, meibomian gland dropouts, OSDI
- The primary visit is week 4 and primary efficacy variables are the FTBUT and quality of meibomian secretions
- A two-sided test with p-value less than or equal to 0.05 will be considered as statistically significant.
- 18. Comparisons between pairs of treatment groups will be done with Cochran-Mantel Haenszel (CMH) tests, stratified by the ocular discomfort strata. Within Strata comparisons will be done with Wilcoxon rank-sum tests for both ordinal and continuous variables. For nominal variables, within strata comparisons will be done with Pearson's chi-square or Fisher's exact tests.
- 19. Exploratory pharmacokinetics data analysis
- Summary statistics of testosterone, dihydrosterosterone, and 3-alphaandrostanediol glucuronide serum concentrations will be calculated. The relationships between treatment time and gender will be examined.

Confidentiality

The identity of the subjects will be treated as confidential. The results of the study, including any other data, may be published for scientific purposes but will not reveal the name of the subject or include any identifiable references to the subject. Although

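### Both primary endpoints are read twice before allocation, but the plan compares change from baseline and adjusts for neither reading

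*Combined protocol and SAP*

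**What the plan says.** The visit schedule has two pre-treatment visits: "Visit 1: Screening visit (Day -14") and, two weeks later, "Visit 2: Baseline (Day 0) : the drug (placebo) is prescribed and dispensed". In "Table 5: Schedule of visits and procedures", the FTBUT and secretion-grade rows are marked at both, and only the Day 0 column is called baseline. The Randomization method section assigns subjects after they pass both examinations, so both readings precede allocation.

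The null hypothesis is framed on change: "There is no difference in change from baseline to week four for either fluorescein breakup time (TBUT") or secretion score. The sample size rests on the same contrast, "comparing the change from baseline in FTBUT in each arm with a two sample t-test". It assumes a "clinically meaningful change of 2.5 seconds with Standard Deviation (SD) following treatment of 2.5 seconds", and concludes: "With the actual power of 0.807, total of 34 subjects with seventeen (17) subjects per arm will be recruited for this study".

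The general statistical methods name ANOVA, Cochran-Mantel-Haenszel tests stratified by ocular discomfort, and Wilcoxon tests. They make week 4 the primary visit and set the threshold: "A two-sided test with p-value less than or equal to 0.05 will be considered as statistically significant". They do not say how the baseline value is built, and neither pre-treatment reading enters as a covariate.

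**The concern.** A raw change score carries the whole error of the baseline reading into the outcome. When the baseline-to-outcome correlation is below 1, adjusting the week-4 value for baseline has smaller residual variance than subtracting baseline. A second pre-treatment reading of the same quantity may reduce it further. Both readings are already collected on every randomised subject, and no adjustment is planned for either.

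What is at stake is precision in a trial of 34 subjects with power just over 0.80 and no stated dropout allowance. There is also a smaller gap. With two pre-treatment readings and no rule for the baseline value, the choice could be made after the data are seen.

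**Working it through.** **Inputs.** From the sample size section and general statistical methods: difference 2.5 s, SD 2.5 s, 17 per arm, two-sided 0.05. From Table 5: readings at Screening (S), Day 0 (B) and week 4 (W). The documents give no between-visit correlations, so those below are assumptions, with equal variance s² at each visit.

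**The plan's own figure.** Exact two-sample t-test power (noncentral t) with standardised difference 2.5/2.5 = 1.0 and 17 per arm is 0.807037, as in Table 2.

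**Formulas** (r_SB, r_BW and r_SW are the three correlations):

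- Raw change from Day 0: 2s²(1 − r_BW)
- Change from the mean of S and B: s²[1 + (1 + r_SB)/2 − (r_BW + r_SW)]
- ANCOVA on Day 0 alone: s²(1 − r_BW²)
- ANCOVA on both: s²[1 − (r_BW² + r_SW² − 2·r_SB·r_BW·r_SW)/(1 − r_SB²)]

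**Worked case, 0.7/0.6/0.5** (r_SB/r_BW/r_SW, in units of s²).

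- Raw change: 2 × 0.4 = 0.80.
- Mean baseline: 1 + 0.85 − 1.10 = 0.75, ratio 0.938.
- Day 0 ANCOVA: 1 − 0.36 = 0.64, ratio 0.80.
- Both: 1 − (0.36 + 0.25 − 0.42)/0.51 = 0.627, ratio 0.784.

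**Variance relative to raw Day 0 change**

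| Assumed r_SB/r_BW/r_SW | Mean of two | ANCOVA, Day 0 | ANCOVA, both | Screening adds beyond Day 0 |
|---|---|---|---|---|
| 0.3 throughout | 0.75 | 0.65 | 0.615 | 5% |
| 0.5 throughout | 0.75 | 0.75 | 0.667 | 11% |
| 0.7 throughout | 0.75 | 0.85 | 0.706 | 17% |
| 0.7/0.6/0.5 | 0.938 | 0.80 | 0.784 | 2% |
| 0.8/0.6/0.5 | 1.00 | 0.80 | 0.799 | 0.2% |
| AR(1), 0.9 per two weeks | 1.08 | 0.905 | 0.905 | 0% |

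**Simple mean.** With equal variances and equal correlations the ratio is 1.5(1 − r)/[2(1 − r)] = 0.75 for any r. If 2.5 s is the SD of change, it becomes 2.5 × √0.75 = 2.17 s and power rises from 0.807 to 0.904. At 0.7/0.6/0.5 power is 0.831, at 0.8/0.6/0.5 it stays at 0.807, and under AR(1) at 0.9 the variance rises by 8%. If the same entry cut applies at both visits, simulation with equal correlations of 0.4 to 0.7 puts the saving at 14 to 21%.

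**ANCOVA on both.** The cut is 33% at 0.5 throughout, 22% at 0.7/0.6/0.5 and 20% at 0.8/0.6/0.5. On the same reading of the 2.5 s, with 30 error degrees of freedom instead of 32, power is 0.93, 0.89 and 0.88. Beyond these three cases the cut runs from 38% (0.3 throughout) to about 10% (AR(1) at 0.9).

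**Cost of fitting.** Chance covariate imbalance inflates the variance of the adjusted difference by about (N − 3)/(N − p − 3) for p covariates. With N = 34 that is 31/30 = 1.033 for one covariate and 31/29 = 1.069 for two. Net of this, the three ratios are 0.713, 0.838 and 0.854, and power is about 0.92, 0.87 and 0.86. For Day 0 alone the net ratios are 0.775, 0.827 and 0.827. So the second covariate gains in the first case and costs 1 to 3 points in the other two.

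**The case against.** The strongest reply is that nothing here is wrong. A single Day 0 baseline gives an unbiased comparison, Table 2 reproduces exactly, and FTBUT at each visit is already the mean of three measurements, so some reading noise is averaged out. That stands: this is a question of efficiency.

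A reader might infer that using the second reading would by itself cut variance by a quarter. The documents do not support that. Screening lies six weeks before week 4 and Day 0 only four. Screening is also a selection visit: a secretion score of at least 8 is required, and FTBUT of 6.0 s or less is one diagnostic route. After it, only study-supplied tears are allowed. Selection and product limits act before allocation and on both arms alike, so they do not bias the comparison, but they can make Screening a weaker predictor of week 4.

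It would also go too far to say that the plan discards the Screening reading or defines change from Day 0 alone. The reading serves eligibility and might serve the exploratory repeatability analysis. Day 0 as the reference follows from a visit label, not from an analysis rule.

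Two more limits stand. The 2.5 s is described as an SD following treatment, so it may not be the SD of change. And the t-test appears only in the sample size section; the analysis section has no week-4 model to extend, so the ANCOVA would be new.

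**Conclusion.** The point holds as a missed efficiency. Both primary endpoints have two readings before allocation, and the planned comparison adjusts for neither. Adjusting the week-4 value for both cuts residual variance by about 20 to 33% against raw Day 0 change at the three main assumed correlation sets, or about 15 to 29% after the cost of fitting. The gain would be smaller if the week-4 value tracks Day 0 very closely. Much of it comes from Day 0 itself. Screening's share is worthwhile if all visits are about equally correlated and close to nil otherwise.

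Power of 0.904 from a mean-of-two baseline is a favourable illustration. It needs equal variances, equal correlations and 2.5 s as the SD of change. A reader might also infer that the trial is mis-sized; it is not, since 17 per arm gives 0.807 for the stated inputs.

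**What to change.** Before unmasking, state in the general statistical methods that the week-4 value of each primary endpoint is compared between arms by ANCOVA, with the same eye's Day 0 and Screening readings as covariates. Do not replace baseline by the simple mean of the two readings, because that can lose precision if Screening tracks week 4 less well than Day 0 does. Record the between-visit correlations assumed.

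The cost is a short paragraph of analysis wording and about two degrees of freedom among 34 subjects. The Screening covariate may add little, and at the less favourable correlations it does not quite repay its own fitting cost. No visit or procedure changes, and the sample size need not change.

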Due to the relatively small sample size (n < 200) and the need to control and balance the influence of covariates, such as age and sex, we adopted the method of covariate adaptive randomization.⁴⁵ With two covariates of sex (2 levels: male, female) and age (2 levels: <50, >50) between study arms (treatment and control), a total of 4 block combinations is produced. After a participant has passed the screening and day 0 examinations, the first 10 participants will be assigned to one of the treatment groups within each block by simple randomization, according to a randomization scheme ([name] [name] will generate this). The next new participant is then sequentially assigned to a particular treatment group by considering the specific covariates and previous assignments of participants. For example, the first 10 participants assignment are broken down by covariates as in Table 3. Then the 11^{th} participant, who is male and >50 years old, needs to be assigned to a group (control vs. treatment). Based on the characteristics of the 11th participant, the method adds marginal totals of the corresponding covariate categories for each group and compares the totals. The participant is assigned to the group with the lower covariate total to minimize imbalance. In this example, the appropriate categories are male and > 50 years old, which results in a total of 6 (3 for male and 3 for >50) for the control group and a total of 5 (3 for male and 2 for >50) for the

treatment group. Because the sum of marginal totals is lower in treatment group

(5<6), the 11th participant is assigned to the treatment group.

Control group		Sex	Marginal total	
		Male	Female	
Age	<50	2	0	2
	>50	1	2	3
Marginal total		3	2	5

Table 3. Procedure of randomization

Treatment group		Sex	Marginal total	
		Male	Female	
Age	<50	1	2	3
	>50	2	0	2
Marginal total		3	2	5

Every participant is assigned a number from 001 to 100 and recorded with the specific number during the whole study until de-identified at the end of the study.

Masking

- 1. The participants will be masked from the assignment of the treatment group.
- An unmasked research assistant will recruit and schedule subjects and administer the questionnaires and exclude subjects based on the above-mentioned inclusion and exclusion criteria.
- 3. Another unmasked research assistant will implement the randomization based on the above covariate adaptive randomization method.

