- 4. The principal investigator is masked from tests and placebo formulation during the follow up dry eye evaluations on subjects.
- 5. All masked information will only be opened at the end of the study or unless an adverse event (AE) requires unmasking to determine whether the AE was due to the treatment medication.

Study Sites

 Southern California College of Optometry at Main Campus ([name]). Main site for dry eye examination

Inclusion & Exclusion Criteria

Inclusion criteria

There are no restrictions for subject inclusion based on ethnicity, race, or occupation. All subjects meet the following criteria:

- 1. Male or female age over 18
- 2. Able and willing to follow study instructions.
- 3. Are able to provide written informed consent
- 4. Written authorization for use or release of health and research study information will be obtained
- Are willing to discontinue use of artificial tears and makeup on the study visit days
- 6. Able and willing to attend the clinical laboratory for morning blood draws to assay serum testosterone in addition PSA levels for men.
- 7. Patient must have a best corrected visual acuity of 20/40 or better in each eye
- 8. Patients must have normal lid position and closure

- Patients' willingness and ability to cooperate with the investigator and follow all instructions
- 10. A negative urine pregnancy test result for women of childbearing potential
- 11. Women of childbearing potential (from 18 to 50 years old) must have a history of bilateral tubal ligation or use contraceptives, implants, injectables, transdermal patch or IUD for birth control during the study. Patients taking oral contraceptives must not miss 2 or more doses in a one-month period. If these methods of birth control do not apply, women of childbearing potential must have a monogamous partner who has had a vasectomy at least 3 months before the screening visit. The date of the vasectomy and physician contact information must be documented in the source documents.
- 12. Subjects must have a meibomian gland secretion score of 8 or greater (0 24 scale).
- 13. Subject s must have at least 50% meibomian glands present in the upper eyelids.

Exclusion criteria

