- Uncontrolled systemic disease or the presence of any significant illness or condition that could, in the judgement of the investigator, jeopardize patient safety or interfere with interpretation of the study results (Sjogren's syndrome and related autoimmune disease are allowed).
- 2. Known or suspected prostate cancer or male patients with a PSA level > 4ng/mL. If PSA level is > 4 ng/mL, the patient can participate only if the patient receives written approval by a urologist. If a man has had a recent prostate exam, at least 4 weeks should separate the prostate exam and our study screen test. If a man has

benign prostatic hyperplasia (BPH), the participants should be notified the risk of worsening BPH if he wants to participate.

- Current or recent venous thromboembolism (VTE), including deep vein thrombosis (DVT) and pulmonary embolism (PE). Evaluate subjects who report symptoms of pain, edema, warmth and erythema in the lower extremity or acute shortness of breath and seek medical care.
- 4. Recent cardiovascular events (e.g., MI, stroke). Subjects who report signs or symptoms of heart attack or stroke should seek medical care.
- 5. Hepatic disorders (hepatitis, jaundice, hepatic cancer et al.). Subjects should monitor for signs or symptoms of hepatic dysfunction (e.g. jaundice)
- 6. Subjects with cancer and at risk for hypercalcemia (e.g., lung cancer, kidney cancer, multiple myeloma, lymphoma, leukemia, ovarian cancer. et al.)
- 7. Subjects taking insulin, warfarin or systemic corticosteroids.
- Contact lens wear during the six months prior to study start and at any time during the study.
- 9. Punctal occlusion done within 3 months of the screening visit or during the study
- 10. Active ocular infection, non-KCS ocular surface inflammation (e.g., episcleritis) or intraocular inflammation (e.g., uveitis)
- 11. Female patient who is pregnant or nursing or planning a pregnancy during the study.
- 12. Males or females with a personal history of breast cancer.

- 13. Patients who are currently on any androgen or anti-androgen treatment or who have discontinued such treatment less than three months prior to the screening visit. Anti-androgen therapy includes medications or supplements that may interfere with testosterone metabolism, such as 5-alpha reductase inhibitors (e.g., finasteride, dutasteride).

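### PSA decides eligibility, but the schedule makes no provision for its result before assignment and dispensing, and the baseline testosterone draw is not timed against first use

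*Combined protocol and SAP*

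**What the plan says.** - **Exclusion criteria, item 2.** A PSA above 4 ng/mL excludes a man, with one exception: "If PSA level is > 4 ng/mL, the patient can participate only if the patient receives written approval by a urologist". After a recent prostate exam, "at least 4 weeks should separate the prostate exam and our study screen test".
- **Visit schedule.** Visit 1 is at Day -14, and no blood test is listed there. The list continues with "Visit 2: Baseline (Day 0) : the drug (placebo) is prescribed and dispensed" and then "Visit 2a: serum blood draw for baseline total testosterone level, hematocrit, lipid panel, PSA for men only at clinical laboratory". Visit 2a has no day and no rule tying it to first use of the gel. Visit 4a does have such a rule: it must be in the morning and no more than two hours from application.
- **Table 5.** The blood row is for sex hormone, marked at Day 0 and week 4 and blank at screening. PSA has no row. The Day 0 column of the drug row reads "Initiate Drug or Placebo".
- **Randomization method.** "After a participant has passed the screening and day 0 examinations, the first 10 participants will be assigned". The paragraph mentions no laboratory result and no urologist approval.
- **Text pointing to testing before treatment.** Under Masking, item 2, an unmasked assistant is to "exclude subjects based on the above-mentioned inclusion and exclusion criteria". Inclusion criterion 6 requires that a subject be "Able and willing to attend the clinical laboratory for morning blood draws to assay serum testosterone in addition PSA levels for men".

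**The concern.** An exclusion criterion works only if the information it needs exists when the decision is taken. Here the decision to assign and supply a man falls at Day 0, and the schedule gives no earlier point at which his PSA is drawn. If the result arrives afterwards and is above the protocol's limit, he has been assigned, and possibly exposed if he is in the test arm, or he must be taken out after randomisation. The first defeats the purpose of the criterion. The second removes someone from a comparison of 17 per arm for a reason that should have been settled beforehand.

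The same visit supplies the baseline testosterone value, from which the week-4 rise is judged. If some subjects have already used the gel by then, the value is not a baseline for those in the test arm.

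**Working it through.** The documents give no figure to recompute on this point, so the check sets the sections side by side.

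**1. When must PSA be known?** Exclusion item 2 makes participation depend on the value or on a written approval. It also speaks of a study screen test, which suggests that testing was intended at screening.

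**2. When is PSA drawn?** Only at Visit 2a. Screening runs from Day -14 to Day 0, which is 14 days, and neither Visit 1 nor the screening column of Table 5 lists a blood draw.

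**3. Does any reading of the undated Visit 2a solve the problem?**

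| Reading of Visit 2a | PSA result or approval before Day 0 dispensing | Testosterone baseline |
|---|---|---|
| Day 0 morning, before first use | Not provided for: 0 days between draw and dispensing for a laboratory result and, if high, a urologist's written approval | Sound |
| Day 0, after first use | Not provided for | Raised in the test arm only |
| A later morning | Impossible: the draw follows dispensing | Raised in the test arm if application began on Day 0, as Table 5 shows |

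The most favourable reading rescues the testosterone sample but not the PSA criterion.

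**4. Is there a hold elsewhere?** The randomisation paragraph requires the screening and Day 0 examinations to be passed and names no laboratory result. Masking item 2 gives someone the task of excluding subjects but no PSA value at that time. Inclusion item 6 concerns willingness to attend, not a result.

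**5. Direction of the testosterone error.** Let B be the true level before treatment, W the week-4 level, and c ≥ 0 the rise already present in a late sample.

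- Test arm: observed change = W - (B + c) = (W - B) - c.
- Placebo arm: c = 0, because the placebo contains no testosterone.
- Any between-arm difference in the rise is therefore understated by c. If every sample precedes first use, c = 0.

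**6. Size of c.** It cannot be derived. The only figure is the simulated mean rise of 0.15 to 0.18 ng/ml, which is for once-daily use. The trial applies gel twice daily, the protocol itself says the effect of that regimen is not yet known, and the time from any first application to Visit 2a is unspecified.

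**The case against.** The best reply is that Visit 2a is a companion visit to Visit 2, not a later step. Visit 4a supports this: it is listed after Visit 4, where the drug is stopped, yet must fall close to an application, and the background text places that draw at the four-week visit. Table 5 also puts the hormone draw in the Day 0 column. This stands. A reader might infer from the list order that the PSA draw necessarily follows dispensing; an undated visit does not support that. A separate medical group dispenses the gel, so the time of hand-over, and hence of first use, is not fixed either.

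A reader might also infer that nothing bars a man with a high PSA from the trial. That is wrong too. The exclusion makes participation conditional, all subjects are to meet the criteria, one assistant excludes and a different one randomises, and the word baseline implies a sample before treatment.

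Two pieces of apparent support are weak. The missing PSA row in Table 5 says little, because the required urine pregnancy test has no row either. The lack of a laboratory step in Procedure I also says little, because passing it leads only to Procedure II, not to assignment.

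What the reply does not answer is that the bar depends on information the schedule does not supply in time. A same-day draw does not by itself make a laboratory result, still less a written approval, available before Day 0 dispensing.

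**Conclusion.** The point holds as an inconsistency between the PSA exclusion and the schedule meant to apply it. Followed as written, the plan could assign and supply a man whom its own criterion excludes. This is more than a missing detail, because even the most favourable timing of Visit 2a leaves no provision for the result.

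The number of men affected cannot be estimated: the documents give neither a rate of PSA above 4 ng/mL nor an expected number of men.

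The testosterone part is conditional. There is no problem if the sample is taken on the Day 0 morning before first use. If it is taken later, the week-4 rise is understated by an unknown amount, and only the exploratory pharmacokinetic analysis is affected. A reader might infer that the efficacy comparison is biased in the same way. It is not: tear breakup time and secretion grade do not depend on this blood sample.

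The conclusion rests on the text available. Some pages and Appendix I were not seen, and the interval between Visits 2 and 2a is not stated.

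**What to change.** Reconcile the visit schedule, Table 5, the randomisation paragraph and exclusion item 2. They should agree with the PSA exclusion the protocol already states, including its written-approval exception, and with the description of the testosterone sample as a baseline. The text should also say what the study screen test in item 2 refers to, and how Visit 2a is timed relative to assignment, dispensing and first application. The sponsor decides that timing; the existing 14-day screening period is available.

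The cost is wording in those places, with no new type of visit. The downside is that some laboratory tests would be done on subjects who then fail screening.
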